To test efficacy, 280 patients with cocaine use disorder will be randomly assigned to: standard care (SC), SC+traditional twice weekly reinforcement, or SC+adaptive VI reinforcement. Evaluations will be completed at baseline and throughout 18 months to assess objective and self-reported indices of drug use, psychosocial problems, and HIV risk behaviors. Primary hypotheses are (1) the adaptive VI reinforcement intervention will improve outcomes relative to standard care during the treatment period and throughout follow-up, and (2) the adaptive VI reinforcement intervention will improve outcomes relative to the traditional reinforcement system. This study will also evaluate the roles of cognitive control and treatment outcome. Patients with better cognitive control are expected to maintain longer durations of abstinence across conditions. If these measures differentially relate to outcomes across treatments, such results suggest the potential of pairing reinforcement interventions to individuals most likely to benefit from them; they may also indicate possible markers of response in a treatment-specific manner. If cognitive indices mediate treatment response, future studies can refine interventions to improve cognitive processes and long-term outcomes.

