**1. Determine the efficacy of an adaptive progressive VI reinforcement intervention for reducing cocaine use in the short- and long-term.** The hypothesis is that patients assigned to the adaptive progressive VI reinforcement intervention will achieve longer periods of abstinence than patients in standard care during the period reinforcement is in effect (24 weeks). We will also evaluate how well this reinforcement intervention maintains benefits throughout follow-up (18 months).

**2. Compare the relative efficacy of adaptive progressive VI reinforcement to a traditional reinforcement intervention.** Patients receiving adaptive progressive VI reinforcement are hypothesized to achieve greater during and post-treatment abstinence than those receiving traditional twice-weekly reinforcement.

Secondary and exploratory aims of the study are to:

**a. Evaluate relations between behavioral and measures of cognitive control and response to monetary rewards and treatment outcomes.** Patients with better cognitive control are expected to achieve longer durations of abstinence, regardless of treatment assignment. Patients who are more sensitive to monetary rewards are expected to achieve longer duration of abstinence, particularly when assigned to a reinforcement intervention. We also expect that sensitivity to monetary rewards and cognitive control may increase among those who are assigned to a reinforcement intervention, and that changes in these processes may mediate drug use outcomes.

**b. Assess the impact of reinforcement interventions on HIV risk and other outcomes.** Compared to SC, reinforcement interventions are expected to reduce high risk sexual behaviors that spread infectious diseases. Reinforcement interventions are also hypothesized to decrease psychiatric symptoms and improve quality of life. Both short-term and long-term effects will be examined. Gender effects will also be explored.

**c. Estimate costs and cost-effectiveness.** We will examine costs and cost-effectiveness of interventions and estimate conditions under which, and patients for whom, these interventions may be most cost-effective.

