*b.) Response to monetary rewards.* Contemporary theories on addiction point to abnormalities in reward circuitry in regions such as the ventral striatum and ventromedial prefrontal cortex (e.g., Chau et al., 2004; Volkow et al., 2003). Volkow et al. (2003) have proposed that, in addiction, the reward value of drugs increases while the reward value of other reinforcers (such as money) decreases. Many studies have shown deficits in reward processing, reflected by reduced response to monetary rewards in the ventral striatum, in substance using patients relative to healthy controls (Balodis et al, 2012; Beck et al, 2009; Peters et al, 2011; Wrase et al, 2007). These findings appear especially relevant to reinforcement interventions, because they provide monetary rewards as alternatives to those derived from drugs. By their nature, these interventions may be particularly beneficial for those who are sensitive to monetary rewards. Therefore, we expect that individuals' neurocognitive responses to monetary rewards pre-treatment may predict treatment outcomes in reinforcement conditions, serving as a potential moderator of treatment effects. Further, because monetary rewards appear to serve as effective reinforcers at least as long as they are in effect, we expect that sensitivity to monetary rewards may increase during treatment, and that this increase may mediate outcomes.

**5. Cost-effectiveness.** We will not only evaluate the efficacy and moderators and mediators of these interventions, but also their cost-effectiveness, as we have done previously (Olmstead et al. 2007abc, 2009). These data will help inform decisions about for whom and under what circumstances funders or society may be willing to pay for their increased costs. As more private providers, state systems (NY, SC), and federal agencies (the VA) are integrating these interventions, this study will provide important and timely data regarding the conditions under which and patients for whom reinforcement interventions engender benefits.

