For cost and feasibility issues, the fMRI study is limited to patients in groups most likely to show treatment differences, Groups A and C. This design most cost-effectively addresses the issue of if, and how, the availability of monetary based reinforcers alter brain functioning. Based on our earlier work (Devito et al., 2012; Kober et al., 2010) and pilot data, we estimate a medium effect size for changes in regions such as VS and PFC regions. Thirty participants per group is sufficient to determine correlations of  $r \geq .30$  between neural activity in Stroop and MID task and outcome variables. We estimate 25 participants post treatment will be sufficient to assess treatment-related changes in neural activity over time (see Devito et al., 2012).

If effects of reinforcement interventions are moderated by cognitive control, future studies may target these interventions toward patients based on cognitive functioning. As reinforcers add known costs, being able to determine those who will be most positively affected will help direct scarce resources toward patients most likely to benefit. If cognitive function mediates outcomes, future research may refine and test therapies that reduce impulsive choices, and improve cognitive flexibility, inhibition and/or control (Bickel et al., 2011). Combining reinforcement with an intervention that improves cognitive control may result in even more durable effects, which may reduce personal-- and societal—harms related to drug abuse.

**Economic Evaluation.** If primary hypotheses are supported, we will conduct cost-benefit analyses. These interventions can be costly, even when reinforcers are relatively modest. Not only must costs of reinforcers be included, but so must administration costs, which include staff time for managing and delivering reinforcers. Despite costs, these interventions may provide benefits to (1) clinics in terms of enhanced reimbursements (Lott & Jencius, 2009), and (2) society in terms of reductions in healthcare services (hospitalizations, ER visits) and criminal justice system costs, and improvements in workplace productivity (Petry et al., in press c). Using data from the PAC-SAT, this study will determine the net benefit of adding reinforcers, from both clinic and societal perspectives. It will also estimate costs of each week of abstinence attributable to the reinforcement conditions.

- a. Comprehensive administrative costs of interventions will be quantified (Olmstead et al., 2007abc;

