Calculation of net benefits. First, resource utilization and cost data will be used to estimate the average net benefit (i.e., benefits – costs) per patient in each intervention from clinic and societal perspectives (Drummond et al., 2005; Zarkin et al., 2008). Second, average net benefits, and confidence intervals around estimates, will be calculated by subtracting average net benefit of adaptive reinforcement from standard care, or adaptive from traditional reinforcement. Finally, sensitivity analyses (Olmstead et al., 2007a; Drummond et al., 2005) will determine the robustness of the net benefit to alternative assumptions about a variety of cost parameters (e.g., unit costs of services, reimbursements received). If reimbursements rise by maximizing the number of patients attending groups via reinforcement treatment, net benefits are higher as shown by Lott and Jencius (2009).

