Cost-effectiveness ratios. If reinforcement engenders net benefits, then it ought to be adopted. However, even in the absence of a net benefit, the incremental cost-effectiveness ratio (ICER) is critical to eventual policy decisions. The ICER is calculated as: (i) incremental costs to (ii) incremental effectiveness (difference between average effectiveness of treatments in terms of weeks of abstinence). Using expert panel recommendations (Gold, 1996; Johanneson, 1996; Weinstein, 1996), we will present traditional ICERs and uncertainty of the ratios (Gold, 1996; O'Brien et al., 1994) and derive a single synthetic measure of multiple indicators of effectiveness, including quality of life (Hargreaves et al., 1997; Rosenheck et al., 1998). We will also conduct acceptability curve analysis to provide policy relevant interpretations (Fenwick et al, 2001,2004; Lothgren & Zethraeus, 2000; Polsky et al., 1997; vanHout et al., 1994). Multiple samples are selected randomly (bootstrapped), with replacement, from the original sample to approximate the larger population. These analyses can also be performed with important subsamples, such as patients with greater sensitivity to rewards if this is determined to be an important predictor of response to reinforcement interventions. Incremental cost and effectiveness values and ICERs can be calculated for each new sample and compared with theoretical "willingness to pay" values for an outcome, such as days abstinent. Such analyses inform policy makers in decision-making (Olmstead et al, 2007ab; Sindelar et al, 2007b) and can be conducted with samples even smaller than those herein (Olmstead et al., 2007c,2009; Sindelar et al., 2007a).

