In sum, this study allows for rigorous determination of costs and benefits of interventions that accrue to clinics and society. A clinic perspective is crucial because, at least in the immediate future, agencies are unlikely to fund expanded services unless they are cost beneficial. Societal perspectives (ICER analyses) are critical for future policy that might allocate state and federal funding to further support reinforcement interventions, as is now being done on a limited basis for substance abuse care as well as in some other health care arenas. Only a comprehensive study such as this can address multiple perspectives, ranging from individual differences in cognitive response to treatments, to clinical and societal effects. The ultimate goal of this proposal, which integrates these perspectives, is to optimize benefits of reinforcement interventions and extend them to the patients most likely to derive clinically significant, and durable, reductions in drug use.

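### The cost-benefit analysis is made conditional on the primary hypotheses being supported, although the economic aim is unconditional and the trigger is undefined

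*Combined protocol and SAP*

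**What the plan says.** Specific aims lists the economic work as aim c, among the secondary and exploratory aims, with no condition: "We will examine costs and cost-effectiveness of interventions and estimate conditions under which, and patients for whom, these interventions may be most cost-effective". The Innovation section repeats the commitment: "We will not only evaluate the efficacy and moderators and mediators of these interventions, but also their cost-effectiveness".

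The Economic Evaluation section begins differently: "If primary hypotheses are supported, we will conduct cost-benefit analyses". Later in the same paragraph the wording is again unconditional: "this study will determine the net benefit of adding reinforcers, from both clinic and societal perspectives". The paragraph also commits to estimating the cost of each week of abstinence attributable to reinforcement. The section's closing summary carries no condition either: "this study allows for rigorous determination of costs and benefits of interventions that accrue to clinics and society".

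Calculation of net benefits plans two contrasts, described as "subtracting average net benefit of adaptive reinforcement from standard care, or adaptive from traditional reinforcement". Cost-effectiveness ratios then says that "even in the absence of a net benefit, the incremental cost-effectiveness ratio (ICER) is critical to eventual policy decisions", and plans bootstrap resampling and acceptability curves.

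Both primary hypotheses are superiority claims. The second, in the opening summary, is "2) the adaptive VI reinforcement intervention will improve outcomes relative to the traditional reinforcement system".

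**The concern.** An aim stated without condition and an analysis section that opens with a condition cannot both be followed as written. Whether patients, clinics and funders get a net-benefit estimate would depend on a test of effect alone. Yet net benefit is a joint quantity of cost and effect with its own uncertainty.

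The problem is sharpest for adaptive against traditional reinforcement. Hypothesis 2 is superiority, so similar effectiveness leaves it unsupported. If both hypotheses are required, the adaptive-versus-traditional net-benefit contrast is then withheld. Design considerations itself argues that twice-weekly attendance may also work but costs more in staff time, testing and prizes. With similar effectiveness, that cost argument is what would be left to decide between the two schedules.

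The trigger is also undefined, so the decision whether to run the analysis would be made after the results are known.

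**Working it through.** The documents give no figure for how often the condition would be met, so there is none to reproduce. The check has two parts.

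**1. Scope of the condition, by comparing the text.**
- The conditional sentence names cost-benefit analyses. Its natural referent is the net-benefit work.
- Aim c and the Innovation section speak of costs and cost-effectiveness, unconditionally.
- The later net-benefit sentence and the closing summary of the economic section are unconditional, so the section conflicts with itself as well as with aim c.
- The ratios are retained when there is no net benefit. That qualifies the net-benefit result and says nothing about the primary hypotheses. The ratios are introduced as a follow-on to the net-benefit result, under the same heading, so whether the opening condition reaches them is open.

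**2. How often the condition would be met.**

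Inputs from Power analyses for primary aims: d = 0.46 for adaptive (C) v standard care (A), d = 0.35 for adaptive v traditional (B), α = 0.05, and 60, 110 and 110 patients in A, B and C. Sidedness is not stated, so both are shown. Assumption: supported means significant in favour of adaptive.

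Standard errors in SD units:
- C v A: √(1/60 + 1/110) = 0.1605, so the mean of z is 0.46/0.1605 = 2.866.
- C v B: √(2/110) = 0.1348, so the mean of z is 0.35/0.1348 = 2.596.
- Correlation from the shared arm C: (1/110)/(0.1605 × 0.1348) = 0.42.

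Power of each test:
- Two-sided (1.960): Φ(0.906) = 0.818 and Φ(0.636) = 0.738.
- One-sided (1.645): Φ(1.221) = 0.889 and Φ(0.951) = 0.829.

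The chance that both are significant comes from the bivariate normal. The chance that at least one is significant is P1 + P2 − P(both): two-sided 0.818 + 0.738 − 0.644 = 0.911 (from unrounded values), one-sided 0.889 + 0.829 − 0.762 = 0.956.

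| Trigger | Two-sided: met / not met | One-sided: met / not met |
|---|---|---|
| Both hypotheses | 64.4% / 35.6% | 76.2% / 23.8% |
| Either hypothesis | 91.1% / 8.9% | 95.6% / 4.4% |

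The 0.46 is the plan's long-term effect. For effects during treatment the plan cites 0.6 to above 1.0. Putting 0.6 or 1.0 in for C v A, with 0.35 kept for C v B, the chance that both are significant two-sided is 72% or 74%, so the condition fails 28% or 26% of the time.

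Smaller Aim 2 effects, both hypotheses required, C v A at 0.46:
- d = 0.20 (assumed): met 29% two-sided, 42% one-sided.
- d = 0 (equal effectiveness): met about 2.5% two-sided, about 5% one-sided.

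If either hypothesis suffices, equal effectiveness does not block the analysis in the same way: 0.818 + 0.025 − 0.0245 = 0.818, so it runs about 82% of the time (two-sided) on the strength of C v A.

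**The case against.** The strongest reply is that this is an ambiguity of scope. Cost-benefit and cost-effectiveness are treated under separate sub-headings. The ratios and the cost per week of abstinence are promised in unconditional words, and aim c is secondary or exploratory. On that reading much of aim c is delivered whatever happens. This stands, and it limits the point to the net-benefit analyses plus an unclear status for the rest.

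Three stronger readings are tempting but not supported.

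- A reader might infer that the whole economic evaluation is withheld after a null result. The conditional sentence does not say so.
- A reader might take 36% as the chance that aim c is lost. It is the chance that the condition fails on one reading: both hypotheses, two-sided significance. The sentence says supported. Where the plan means a significance condition, as in its mediation analysis, it says so. Other readings go down to 4%.
- A reader might infer that running the analysis only after significance makes the cost per added week of abstinence look about 15% too low, because the selected Aim 2 effect averages 0.41 when the truth is 0.35. The step from effect to cost ratio fails. It needs a fixed, positive incremental cost, whereas prizes are earned per negative sample and so rise with abstinence. The sign of the adaptive-versus-traditional cost difference is not known either. Twice-weekly attendance is said to add cost, while cell service is charged to the adaptive arm only.

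That the analysis matters most when the two schedules perform alike is a judgement. The plan's cost argument supports it, but the plan does not state it.

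**Conclusion.** The point holds in limited form. The plan conditions its cost-benefit analyses on the primary hypotheses, in conflict with aim c, the Innovation section and its own later unconditional sentences. It leaves open which analyses are covered, which hypotheses count and at which time point.

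At the long-term planning effects the net-benefit analysis would be withheld between about 4% and 36% of the time, depending on the reading. If both hypotheses are required and the two reinforcement schedules are equally effective, it would be withheld about 97.5% of the time (two-sided). These figures assume that supported means statistically significant, normal-theory tests, full recruitment at 60/110/110 and no loss to follow-up.

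No primary result or sample size is affected. The change is worth making because it lets the trial answer a question it has set itself.

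**What to change.** Delete the conditional clause at the start of Economic Evaluation. State instead that costs, net benefit, incremental cost-effectiveness ratios and acceptability curves will be estimated for adaptive reinforcement against standard care and against traditional reinforcement, whatever the primary test results. The confidence intervals and bootstrap uncertainty should be those already planned under Calculation of net benefits and Cost-effectiveness ratios. No new method is needed.

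The cost is additional economic analysis if the primary results are null, including the unit-cost and staff-time work described in the section. The Service Utilization Form is scheduled at baseline and at every follow-up whatever the results, though in abbreviated form after baseline. The section also relies on the PAC-SAT, which the assessment schedule does not list. The team should confirm which instrument supplies the resource-use data, a question that arises whether or not the condition is kept.

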### Specific aims

Designed and tested using the NIH Stage Model of psychotherapy development (Onken et al., in press), reinforcement interventions hold great potential to improve drug abuse treatment outcomes. Community clinics are increasingly applying these interventions, but methods to maintain their benefits long-term are needed. Extending **the effects of reinforcement interventions would be a major step forward in increasing the efficacy and acceptability of this approach.** Traditional approaches toward reinforcement, requiring frequent clinic attendance, limit acceptability among both patients and providers, especially when applied over long durations. We have pilot data suggesting the efficacy of a gradually increasing variable interval (VI) reinforcement schedule in maintaining behavior gains. This study will evaluate this approach for improving short- and long-term drug use outcomes. It will also address potential cognitive mechanisms of action.

In total, 280 patients initiating treatment for cocaine use will be randomized to: standard care (SC), SC + traditional reinforcement, or SC + progressive variable interval (VI) reinforcement. The two reinforcement interventions will provide the same overall average maximum magnitudes of expected earnings. Patients in the traditional reinforcement condition will earn reinforcers twice weekly for submitting stimulant negative samples. Patients in the progressive VI reinforcement condition will earn reinforcers for providing cocaine-negative urine samples according to an increasing VI schedule; monitoring and reinforcement will occur

relatively infrequently when abstinence is maintained but increase in frequency if drug use occurs. Cell phones will maintain contact with patients in all conditions to inform them of randomly selected urine testing days throughout a 24-week period to provide, for one of the first times, objective indicators of relapse following treatment cessation. All patients will complete cognitive assessments pre, mid and post-treatment.

Primary study aims are to:

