Although some patients have their own cell phones, >90% of those with phones have pre-paid or government-limited plans, resulting in highly unreliable service (most quickly use up all their minutes). In an informal survey, 93% stated that patients would submit samples up to twice weekly for 6 months in exchange for unlimited cell service. Patients who prefer to use their own cell may elect to receive a \$25 gift card for each month during which they do not miss more than one randomly selected test day in a row. (Patients with their own phones may switch to study phones at any time to ensure contact). If a study phone is turned off, it will be reinstated as soon as the patient submits a sample (i.e., the patient comes to the clinic or UCHC to submit a sample on their own, without being prompted to do so). After discontinuation of cell service, patients will be informed in writing about how to reinstate it. Once cell service is reinstated, similar rules related to continued use will be applied (and service discontinued if they miss >1 prompted test day in a row).

As in all our studies, research will be separate from clinical care. The clinics rarely test for drug use, and only upon suspicion. Clinic-requested samples will occur separately from research samples, and results not shared, as arranged previously (Petry et al., 2011a, 2012a). RAs will congratulate patients for each drug for which they test negative, and if positive, encourage them to discuss any use in group (Human Subjects).

We expect that most patients will not continue in treatment at the clinics for 24 weeks, and median length of stay is <5 weeks. Although prompting sample submission via cell phones will increase sample submission, we expect any effect related to enhancing clinic group attendance will be modest. For >15 years, patients in our studies have been returning to clinics for study procedures (sample submission, follow-ups),

which are clearly differentiated from treatment procedures. Even if these procedures do enhance clinical services received, the effects will be similar across groups as all receive the same incentives for sample submission (i.e., cell service).

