Patients in this condition, as in Group A, will receive a study cell phone (or \$25/month toward their own cell phone service) if they maintain contact with research staff and submit samples when requested to do so. Because the reinforcement schedule for abstinence is set at twice weekly for 24 weeks, there is little reason to inform patients of reinforcement days throughout the study period. However, RAs will phone or text patients at the same frequency in this condition as in Groups A and C to inform them when "a sample is due to maintain cell phone service." If they fail to submit a sample when prompted, additional samples will be requested within the next week, as described in Group A. If two requested samples in a row are missed, then cell service will be discontinued. Reinstatement of cell service will be as described above.

In this manner, reinforcement for submission of negative samples is similar to that provided in traditional reinforcement interventions (pre-determined frequent urine testing). At the same time, prompting of urine sample submission (along with cell phone service for complying with submission) will be similar to other groups so that overall the same minimum number of samples should be obtained across conditions. In this manner, objective indicators of relapse to drug use will be obtained similarly across groups (see also Analyses).

Patients in this group can earn draws for providing negative samples in response to a cell phone prompt, and they may not have submitted these samples had they discontinued care in a traditional reinforcement intervention. In this sense, Group B is somewhat enhanced relative to traditional reinforcer interventions, and allows for a conservative test of Aim 2. Nevertheless, maximum draws per sample is only 1 when patients fail to submit negative samples twice weekly in this condition. Thus, the additional reinforcement for submission of samples by integrating cell phone prompted samples appears modest and unlikely to impact outcomes.

**C. Standard care + progressive VI reinforcement.** These patients receive standard care and earn draws with chances of winning prizes for submitting negative urine samples. However, relative to Group B, the frequency with which they are expected to submit samples to earn abstinence reinforcement decreases over time so long as they maintain abstinence. In the first phase, twice weekly samples are expected just like the other groups,

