
Rosenheck et al, 1995; Sindelar et al. 2007ab), including costs of prizes, mileage for purchasing them, and toxicology tests and management (personnel time to arrange testing and reinforcers in both reinforcement conditions, along with costs of cell phone service in the adaptive reinforcement condition only). Costs related exclusively to data collection (arranging for collection and testing of urine samples when it is not reinforced, RA salaries for data collection) will not be included, as they would not be relevant if interventions were applied clinically. Costs for usual clinical services and clinic reimbursement for same will be ascertained.

b. General healthcare costs will be estimated by multiplying service units used per patient by average unit costs. In- and out-patient, day hospital, aftercare and emergency room services will be estimated from CT claims data, and nationally from the Market Scan database, which estimates service costs.

c. Criminal justice (CJ) system costs. Patients receiving reinforcement interventions may have reduced involvement with the CJ system. The PAC-SAT assesses services provided as well as police contacts, court hearings, and incarceration, along with timing of events that resulted in service use so acts occurring before study participation can be separated from those occurring during it in terms of resource utilization. Unit costs of services will be estimated from national reports (Pastore & Maguire, 2003; US Dept. of Justice 2006).

Other societal costs will be obtained on productivity (earnings and workdays affected by drug use) and automobile crashes (including property damage, injuries, and fatalities).

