- c. Potential Benefits of the Proposed Research to the Subjects and Others. The anticipated benefits to patients in the study include careful evaluation of their medical and psychiatric status, drug and alcohol use, and a potential for reducing their cocaine use. Patients in all groups will receive \$35 in gift cards for the baseline assessment, and \$50 for all others, plus \$25 in gift cards for computer/impulsivity assessments (as well as the chance to win an additional \$5 based on task responses). Patients will receive \$25 for returning the cell phone in working condition. They will receive a study-paid cell phone (or \$25 per month in the form of gift cards to be given at the 3 and 6 month assessments, if they choose to use their own phone, for a total of \$150) so long as they provide study-requested samples, estimated average of 18-23 per patient. Depending on group assignment, patients may also receive prizes for submitting stimulant negative samples. Payment for participation in the fMRI sub-study is \$100 per completed session, pro-rated to \$20 per hour for incompleting sessions, to a maximum of \$200 in total for two completed sessions.

Benefits to society include a potential improvement in the effectiveness of treatment for patients with substance use disorders.

- d. Importance of the Knowledge to be Gained. The potential risks of these treatments are minor compared to the risk incurred by patients with cocaine use disorder. The risk/benefit ratio appears favorable.
- e. Women/Minorities/Children. We expect the gender and racial composition to reflect the demographics of the clinic members. About 50% of patients at each clinic are female, and >45% are members of ethnic minorities (30% African American and 15% Hispanic, all of whom are fluent in English as treatment is only provided in English at these clinics, and 2% Native American, Asian American, or other). These proportions allow for exploratory analyses of gender and racial/ethnicity effects, as we have done previously (e.g., Montgomery et al., 2012).

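### Cell phone service is costed in the adaptive arm only, so the adaptive v traditional cost-effectiveness ratio takes Group B's effect with the phone and its cost without it

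*Combined protocol and SAP*

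**What the plan says.** Item a of the Economic Evaluation lists the administrative costs to be counted: prizes, mileage to buy them, toxicology tests, and staff time in both reinforcement conditions, "along with costs of cell phone service in the adaptive reinforcement condition only". The next sentence leaves out costs that serve data collection alone, on the ground that they would not arise in clinical use.

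The phone itself is not confined to Group C. The Specific aims state: "Cell phones will maintain contact with patients in all conditions". The description of Group B says: "Patients in this condition, as in Group A, will receive a study cell phone", or $25 a month toward the patient's own service. The Human Subjects section, under Potential Benefits, gives the own-phone alternative as $25 "per month in the form of gift cards to be given at the 3 and 6 month assessments", $150 in total.

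The Group B text acknowledges that the phone can affect that arm: "Patients in this group can earn draws for providing negative samples in response to a cell phone prompt". It adds that, under a traditional programme, people who had left care might never have given those samples. It concludes that "Group B is somewhat enhanced relative to traditional reinforcer interventions", then judges the extra reinforcement modest and unlikely to affect outcomes.

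The paragraph on cost-effectiveness ratios divides incremental cost by incremental weeks of abstinence. The paragraph on net benefits plans sensitivity analyses on cost parameters, with unit costs and reimbursements as examples. Neither mentions which arms are charged for the phone.

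**The concern.** An incremental ratio is interpretable when cost and effect describe the same programme. For Group B they do not: the weeks of abstinence come from patients who held a phone and were prompted, while the cost is that of a programme without one. Omitting the phone from Group B is defensible as a picture of routine practice, but the effect in that picture would be Group B's effect without prompts, and no arm supplies it.

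The choice can matter for C v B because maximum prize value is matched by design. At equal performance, the intervention-cost difference then rests on the extra tests in Group B set against the phone charge in Group C. Its sign helps decide whether adaptive reinforcement, if better, is also cheaper or is better at a price. The Design considerations argue that twice-weekly attendance adds substantially to cost; charging the phone on one side works against showing that.

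**Working it through.** **Inputs from the protocol**
- Phone: $25 a month, $150 in total (Human Subjects, Potential Benefits). This is the own-phone payment, used as a proxy because the cost of study service is not stated.
- Samples: 48 in Group B and at least 18 in the other groups (Data Analysis). Potential Benefits estimates an average of 18 to 23 requested.
- Maximum draws: 229 in Group B, worth $460 on average; about 231 in Group C.
- Earlier submission: 14.8 samples in the arm of the ongoing trial reinforced for all 12 weeks (Preliminary studies).

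**Assumptions**
- Cost per sample, c (test plus handling), is not given and is left free.
- Where Group B submits less than its full schedule, I take 14.8 of 24 (twice weekly for 12 weeks), about 62%, so 48 x 14.8/24 = 29.6 samples.
- Equal performance in the two arms, with the prize gap held at its maximum-draw value.

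**The plan's own figures**
- Phone: 25 x 6 = $150, as stated.
- Group B draws: 1+2+3+4 + 44 x 5 = 230, against 229 stated.
- Group C draws over 18 samples: (1+...+6) + (7+9+...+23) + 3 x 25 = 21 + 135 + 75 = 231, as stated.
- Prize gap: 460/229 = $2.01 per draw, so 2 draws are about $4.

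**Cost difference per patient**

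C - B = 4 + P - (nB - nC) x c

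P is $150 if the phone is charged in Group C only. It is $0 if charged in both arms or in neither, provided service lasts equally long in both.

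At 48 v 18 samples (gap 30):

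| c | Phone in C only | Both arms alike |
|---|---|---|
| $2 | +$94 | -$56 |
| $5 | +$4 | -$146 |
| $10 | -$146 | -$296 |

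**Break-even cost per sample with the phone in C only:** (150 + 4.02)/(nB - nC)
- 48 v 18: 154.02/30 = $5.13
- 48 v 23: 154.02/25 = $6.16
- 29.6 v 18: 154.02/11.6 = $13.28
- 29.6 v 11.1 (the same 62% in Group C): 154.02/18.5 = $8.33

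Above break-even, Group C is cheaper under either rule. Below it the two rules disagree, down to a trivial lower limit (4.02/30 = $0.13 at 48 v 18), under which Group C is dearer either way. If service lapses and averages 60% of $150, which is $90, break-even at 48 v 18 falls to 94.02/30 = $3.13.

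**Effect on the ratio.** The shift is $150 divided by the extra weeks of abstinence: $150 per week for a one-week gain, $75 per week for two. This occurs whether or not the sign changes. The $150 is about a third of the $460 expected maximum prize cost (150/460 = 0.33).

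**The case against.** The strongest defence is that the rule is deliberate. In Group C the call or text delivers the variable schedule, so the phone is part of the intervention. In Groups A and B it mainly secures comparable samples for research, and the Group B text says a fixed twice-weekly schedule gives little reason to prompt. Charging the phone only where practice would need it follows the stated costing principle. That stands, and it is why the planned costing should remain the base case. It does not supply an effect for Group B without the phone.

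A reader might infer that the phone produces Group B's results. The documents do not show this. They acknowledge a possible contribution and judge it modest, because draws fall to one per sample when the twice-weekly schedule is not kept. That is a judgement, not an estimate, but the opposite is not established either.

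A reader might also infer that the accounting favours the adaptive arm. It does the reverse: the charge falls on Group C, and any benefit from the phone raises Group B's effect.

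Finally, the sensitivity analyses are an open list, and setting Group C's phone cost to zero gives the same C minus B difference as charging both arms. The plan therefore permits the check, but does not commit to it.

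**Conclusion.** The mismatch is real but limited. Group B's cost and effect are on different bases in C v B, and the rule moves the cost difference by up to about $150 per patient against the adaptive arm, less where service lapses.

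It would go too far to say that the rule decides which arm looks cheaper. A change of sign needs a cost per sample below about $5 at 48 v 18 samples, or about $13 at an assumed 29.6 v 18, and the protocol gives no such cost. Both limits rest on equal performance and on the $150 proxy. Only maximum prizes are matched. Realised prizes, extra tests after a lapse in Group C, and the healthcare, criminal justice and productivity terms will also move the totals.

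The point does not extend to C v A. Standard care in practice is not described as supplying a phone, so charging all arms would cancel a real cost of adopting the adaptive programme.

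The economic evaluation is among the secondary and exploratory aims, and the cost-benefit work goes ahead only if the primary hypotheses are supported. This is a minor improvement that leaves the primary analysis untouched.

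**What to change.** Keep the practice-perspective costing as the base case. In the paragraph on calculation of net benefits, pre-specify one as-delivered sensitivity scenario, for C v B only, that charges phone service in both reinforcement arms at the months actually provided. For the difference this is nearly the same as charging neither arm; it departs only if service lasts longer in one arm. Carry the scenario through to the C v B cost-effectiveness ratio, report it beside the base case, and call the C v B conclusion robust only if the two agree. State that in the base case Group B's effect was measured with the phone in place.

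The cost is one extra costing scenario and no new data. The downside is that the C v B conclusion may be less definite if the two scenarios differ.
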